2.0 Purpose

The purpose of this post approval study is to characterize the chronic performance of the SJM Optisure family of HV leads in patients that have an approved indication, as per ACC/AHA/HRS/ESC guidelines, for implantation of an ICD or CRT-D system for treatment of heart failure or life-threatening ventricular tachyarrhythmia, and who meet all the inclusion/exclusion criteria. The Optisure lead study will be performed in compliance with the Conditions for Approval as agreed upon with the FDA. If during the course of the study a future generation of the Optisure RV lead is approved, these devices may be included in the study upon agreement with the FDA.

The following objectives will be evaluated in the post approval study:

1. To determine the Optisure lead related complication free rate at 5 years
2. To document all Optisure lead related adverse events

Additionally, the following objectives will be evaluated in a subset of patients in the Optisure lead study who agree to participate in a sub-study:

1. To determine the incidence of externalized conductors after enrollment
2. To determine the incidence of other visual lead anomalies by each subcategory per Appendix A after enrollment
3. To determine the incidence of electrical dysfunction[§] after enrollment
4. To evaluate the 30-day adverse event rate associated with lead revision procedures (include lead extractions or abandonments with or without lead replacement)
5. To determine the prevalence of “other insulation anomalies” in returned Optisure leads:
 - Internal abrasion short under RV shock coil
 - Internal abrasion short under SVC shock coil
 - Exposed conductors defined as a breach of the outer insulation and/or breach of the internal silicone lumen tubing, but the conductor cable is contained within the lead body diameter.

[§]”Electrical dysfunction” is determined to be present after adjudication of the following cases of potential electrical failures that led to the lead being either surgically capped/extracted or electrically abandoned. Potential electrical failures include the following:

- Presence of non-physiologic noise not due to external interference
- Rise in pace/sense (p/s) conductor impedance to $> 2000 \Omega$ or increase of more than 200Ω over previous 6 months or increase of 400Ω over any period of time
- Decrease of more than 200Ω over previous 6 months or to impedance $< 200 \Omega$ from baseline impedance $> 300 \Omega$ or decrease of 400Ω over any period of time

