5.3.9 Time from other visual lead anomalies by each subcategory to clinical intervention

Lead Population

All Optisure leads with other visual lead anomalies (by each sub category).

Analysis:

Time to clinical intervention will be analyzed using the Kaplan-Meier method. The zero time will be the date at which other visual lead anomaly (by each subcategory) was detected. Those patients who experience other visual lead anomaly (by each subcategory) after enrollment but do not experience clinical intervention will be censored 3 years after enrollment in this trial.

5.3.10 Comparison of patients with lead compromise as evidenced by imaging (includes externalized conductors and other visual lead anomalies) to those without lead compromise

Patient Population

All the patients implanted with Optisure leads.

Analysis

Demographic and clinical parameters will be compared between patients who experience lead compromise as evidenced by imaging and those who do not experience lead compromise. Specifically, the variables age, gender, body mass index, lead size, lead model, and implant factors such as venous access site, number of other leads in the vasculature, fixation location in the right ventricle, level of activity (based on functional NYHA class scale I, II, III, IV), level of therapy that patient received (no ATP/shock, ATP or shock) and slack (grades 0, 1, 2, 3, 4 based on the scale described by Ha et al., 2010⁸) in the lead will be used for the comparison. Continuous variables such as age or body mass index will be compared using Student's T-tests while categorical variables such as gender or lead models will be compared using Pearson's Chi-square statistic. Point estimates and p-values will be provided from these analyses.

5.3.11 Comparison of patients with electrical dysfunction to those without electrical dysfunction.

Patient Population

All the patients implanted with Optisure leads.

Analysis

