6.0 Analysis and Reporting

6.1 Interim Reports and Trend Analysis

Interim reports will be submitted to FDA every 6 months for the first 2 years and yearly thereafter.

The observed number of enrollments in the study and the sub-study at participating centers, number of implants at participating centers and number of overall US implants will be included in the progress reports until enrollment is completed.

Other data summarized in the progress reports will include:

- Demographic data including gender, age, NYHA functional classification, left ventricular ejection fraction, and indication for device. Continuous variables will be summarized by average and standard deviation. Categorical variables will be summarized by frequency and percentage
- Complications and observations related to the Optisure RV lead will be summarized and reported
- Complications or observations that are unrelated to the RV lead (shown in Table 2) will be summarized and reported
- Signal amplitude measurements for Optisure leads at implant/enrollment, as appropriate, and at each follow-up visit (if available) will be summarized and reported.
- Capture thresholds for Optisure leads at implant/enrollment, as appropriate, and at each follow-up visit will be summarized and reported.

- Pacing lead impedance for Optisure leads at implant/enrollment, as appropriate, and at each follow-up will be summarized and reported.
- High voltage lead impedance for Optisure leads at implant/enrollment, as appropriate, and at each follow-up will be summarized and reported.
- The rate of successful Optisure RV lead implants will be reported (only applicable to patients enrolled at or before implant)
- Total implant procedure time (skin to skin) – the average and standard deviation for successful Optisure lead implants will be reported (only applicable to patients enrolled at or before implant)
- Implant approach (site of venous access) (only applicable to patients enrolled at or before implant)
- Percentage of leads with externalized conductors, other visual lead anomalies at different time points (24, 36, 48 and 60 months)
- Type, location and extent of externalized conductors and other visual lead anomalies
- Percentage of leads with electrical dysfunction in the sub-study
- Prevalence of “other insulation anomalies” in returned Optisure leads

Table 2: Complications or Observations That Are Unrelated To the RV Lead

Pneumothorax

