9.0 Study Procedures

All required study procedures at each specified interval are outlined in the sections below.

Table 3: Schedule of Evaluations Summary

Evaluation	Enrollment*	Every 6 months thereafter until 5 years	24, 36, 48 and 60 month follow-up visits
Inclusion/Exclusion Criteria Evaluation	√		
Record capture threshold, signal amplitude, pacing lead impedance and high voltage lead impedance measurements on Optisure lead	√	√	
RV Lead Handling Characteristics (only applicable to patients enrolled at or before implant)	√		
Cinefluoroscopy (AP, LAO 45° or the best possible LAO view, RAO 45° or the best possible RAO view)			√**

* Enrollment can occur up to 30 days post implant

**Only applies to patients participating in the sub-study

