9.3 System Revisions – if applicable

If the system revision procedure occurs more than 3 months after implant then obtain cinefluoroscopy views of the entire length of the implanted leads before repositioning or explanting the Optisure lead. Cinefluoroscopy should be performed in three views (AP, LAO 45° or the best possible LAO view, RAO 45° or the best possible RAO view) and submitted to St. Jude Medical. If the patient is unwilling then the imaging is not required.

For all lead revisions (e.g. replacement or repositioning of the lead) complete the applicable testing as outlined in section 9.2.1. Any explanted pulse generator or leads (including damaged leads, lead segments and lead fragments) should be returned to St. Jude Medical for analysis promptly.

Any changes to the status of a lead (i.e., capped, removed) will be documented on the Product Out of Service Case Report Form. Complete an Adverse Event (if applicable), System Revision, Imaging (if applicable), and Out of Service for any product used but not implanted (e.g. contaminated, dropped or opened in error) Case Report Form. Submit the forms to St. Jude Medical using the EDC system.

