***Notes**

1. If patient is in atrial fibrillation or atrial flutter or RA lead is turned off, RA electrical measurements are not required.
2. If patient is pacemaker dependent, RV sensing amplitude is not required.

3. As referenced under the Definitions in section 4.2, abnormal pacing lead impedances are defined as measured pacing impedances with values $\leq 200 \Omega$ or $\geq 2000 \Omega$. RV lead pacing impedances have been observed in typical clinical settings to be in the range of 200-1200 Ω for the majority of patients. However, lead pacing impedances measured up to 1999 Ω are considered to be within the normal bounds of the performance of the RV lead because characteristics such as non-viable myocardium, lead-to-tissue contact, etc., specific to each patient have been known to produce measured pacing impedances that are higher than the observed 1200 Ω noted above.

Device diagnostics and archives of RV lead impedance values may also be used to diagnose potential lead failures. Alternatively, investigators should consult the respective device and lead user manuals, St. Jude Medical technical support or other St. Jude Medical clinical support personnel to diagnose potential lead failures.

In the subset of patients participating in the sub-study, cinefluoroscopy (AP, LAO 45° or the best possible LAO view, RAO 45° or the best possible RAO view) of the entire lead length and the pocket area will be performed at the 24, 36, 48 and 60 month visits. Additionally, query the patient to determine whether the patient has had any chest x-rays or fluoroscopy of the implanted leads since the last visit. Whenever possible, obtain copies of any imaging done (x-ray or fluoroscopy). Review those images for signs of lead conductor externalization. Report those events, as applicable, on an adverse event form. Also, query the patient regarding any adverse events occurring between routine visits. Complete a Follow-up Case Report Form and record all results. Should any adverse event occur, complete an Adverse Event Case Report Form. If any images were obtained (especially for patients participating in the sub-study at the 24, 36, 48 and 60 month visits), complete an Imaging Case Report Form. Submit the forms to St. Jude Medical using the EDC system.

Upload the device session record including all stored IEGMs to St. Jude Medical using the SJM EDC Portal device data upload utility.

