19.0 Committees

19.1 Cinefluoroscopy Adjudication Committee

Cinefluoroscopy Adjudication Committee (CAC) will be comprised of at least three Electrophysiologists or Cardiologists specially trained in using Cinefluoroscopy in this patient population. The role of the CAC is to adjudicate the cinefluoroscopy videos/images to determine the presence of lead compromise in the sub-study patient population. Committee members will be reviewing the cinefluoroscopy videos/images for the 24, 36, 48 and 60 month follow-up visits and any additional cinefluoroscopy videos/images

received during the course of the study. Data will be sent either electronically or on a disk to the committee members. Once the adjudication is complete, a cinefluoroscopy adjudication form will be collected per patient per study visit. If the presence of externalized conductors is deemed to be ‘indeterminate’ then the cinefluoroscopy will be further reviewed by two other CAC members. Sample pictures/fluoros/x-rays and other examples of “other visual lead anomalies” will be provided to the adjudication committee to aid the committee members in identifying these “other visual lead anomalies” on the cinefluoroscopy videos/images received from the site.

Only the adjudicated imaging data will be included in the progress reports. Percentage of leads with compromise, evidenced by imaging, will be presented in the report. The type, extent and location of lead compromise, as described in Appendix A, will also be included. As detailed in Appendix A, the HV lead is divided into different regions. Both the proximal as well as distal ends of externalization will be recorded by the cinefluoroscopy adjudication committee. The distribution of externalization (both absolute number and percentage) by each region of the lead will be presented for both proximal and distal ends of externalization. The distribution of “other visual lead anomalies” (both absolute number and percentage) by each region of the lead and each individual subcategory of “other visual lead anomalies” will be presented. The frequency (both absolute number as well as percentage) of individual subcategories will be reported for “other visual lead anomalies”.

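### Sections 5.3.10 and 5.3.11 compare all implanted patients, although lead compromise and electrical dysfunction are systematically ascertained only in the 417-patient sub-study

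*Protocol*

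**What the plan says.** Sections 5.3.10 and 5.3.11 of the protocol belong to section 5.3, the sub-study outcome measures. Each gives its population as "All the patients implanted with Optisure leads", splits it into patients who do and do not have the finding, and promises point estimates and p-values from t-tests and chi-square tests on about a dozen demographic, lead and implant factors.

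Elsewhere the protocol limits where these findings can be established:

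- Section 2.0 says the sub-study objectives are "evaluated in a subset of patients in the Optisure lead study who agree to participate in a sub-study". It defines electrical dysfunction as "determined to be present after adjudication of the following cases of potential electrical failures", in leads that were capped, extracted or electrically abandoned.
- Section 9.0, Table 3, footnotes cinefluoroscopy at months 24, 36, 48 and 60: "Only applies to patients participating in the sub-study".
- Section 19.1 gives the imaging committee the role "to determine the presence of lead compromise in the sub-study patient population".
- Section 19.2 gives the electrical committee the corresponding role for sub-study patients only, reviewing leads removed from service there. Section 6.1 accordingly reports "Percentage of leads with electrical dysfunction in the sub-study".

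Outside the sub-study, images arise only for cause or by chance. Section 9.3 reads "If the system revision procedure occurs more than 3 months after implant then obtain cinefluoroscopy views", and section 9.4 asks sites to collect copies of other imaging where they can.

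**The concern.** A comparison of patients with and without a finding needs the finding to be looked for in the same way in everyone compared. Here the named population is about four times the size of the group in which it is looked for, and the protocol gives no third category for patients who were not assessed.

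In 5.3.10 two kinds of patient enter the *without* group unverified: all main-study patients with no image, and sub-study patients who leave before the first scheduled image at month 24. The few images from outside the sub-study come mainly from revised leads, so cases there are found selectively.

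In 5.3.11 the gap is narrower. Dysfunction requires a lead taken out of service, so a lead still in service is correctly *without*. But main-study leads taken out of service are never adjudicated, and would be counted as *without* for that reason alone.

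The main risk is selection rather than dilution. The *with* group consists almost entirely of sub-study participants, while the *without* group consists mostly of other patients. Any characteristic associated with joining the sub-study, such as age, NYHA class or lead model, can then appear to be associated with lead compromise or dysfunction.

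**Working it through.** **Inputs from the protocol.** Main study 1725 (section 4.1); sub-study 417, five-year attrition 52%, target of 200 with a month-60 image (section 4.3); first scheduled image at month 24 (Table 3).

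**The plan's own figures reproduce.** 200 / (1 − 0.52) = 416.7, rounded up to 417. 828 / (1 − 0.52) = 1725. Neither is in dispute.

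**Who is assessed in 5.3.10.**

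- No scheduled imaging: 1725 − 417 = 1308, and 1308 / 1725 = 75.8%.
- Still in the sub-study at month 24, if the 52% attrition accrues at a constant rate: 417 × 0.48^(2/5) = 311, so 417 − 311 = 106 leave before any scheduled image. Building the loss from the protocol's separate rates gives the same: 17.7% deaths and 9.5% other withdrawals by month 24 combine to 25.5%, and 417 × 0.745 = 311.
- No scheduled image in total: 1725 − 311 = 1414, and 1414 / 1725 = 82.0%.

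**Who is assessed in 5.3.11.** The protocol gives no rate of leads taken out of service; take 3.5% to 10% as an assumption. Main study: 1308 × 0.035 = 46 to 1308 × 0.10 = 131 leads, unadjudicated. Sub-study: 417 × 0.035 = 15 to 417 × 0.10 = 42 leads, adjudicated. At any common rate, 76% of such leads are not adjudicated.

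**Size of a spurious association.** Suppose 2% true compromise everywhere, all 417 assessed, no case found outside, and a factor unrelated to compromise present in 50% of sub-study patients and 40% of the others. Among cases its prevalence is 50%. Among *without* it is (417 × 0.98 × 0.5 + 1308 × 0.4) / (417 × 0.98 + 1308) = 0.424. The odds ratio is 1 / (0.424 / 0.576) = 1.36 where the truth is 1. With 45% outside it is 1.16; with 30% it is 1.88.

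**False-positive rate.** Simulation with 40,000 trials per cell: factor independent of the outcome, uncorrected Pearson chi-square at 5%, unassessed patients coded *without*. Incidences and factor splits are assumptions, because the protocol gives neither.

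5.3.10, 311 imaged, no cases found among the rest:

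| Factor prevalence, sub-study / outside | Incidence 1% | 2% | 5% | 10% |
|---|---|---|---|---|
| 35% / 30% | 5.2% | 5.2% | 6.8% | 8.1% |
| 40% / 30% | 6.7% | 7.0% | 10.8% | 16.3% |
| 50% / 30% | 8.8% | 14.7% | 25.8% | 43.5% |

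- For-cause imaging finds 10% of outside cases, 40/30 split, 5% and 10% incidence: 8.4% and 10.7%.
- For-cause imaging finds 25% of them: about 7% to 8%.
- Same tests in imaged sub-study patients only: 2% to 5%.
- Equal prevalence inside and outside (30/30): about 4% to 5%, no inflation.

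5.3.11, all 417 sub-study patients covered, dysfunction 1%, 2% and 3.5%: 40/30 split 7.0%, 8.2%, 10.7%; 35/30 split 4.9%, 5.6%, 6.8%.

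Repeat runs agree with these figures to within about one percentage point.

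**The case against.** The strongest reply is that the section heading governs. Both items sit under the sub-study outcomes, and several neighbouring items (5.3.5 to 5.3.9) also name their leads without repeating the restriction, so the population line may be loose wording for all implanted sub-study patients. That may well be the intent. But 5.3.1 to 5.3.4 do state the restriction, and an analyst who follows 5.3.10 or 5.3.11 as written would use everyone.

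Second, no sentence says that unimaged patients are coded *without*. This is correct: it is an inference from a two-group comparison over a population that includes them. A later analysis plan could add a rule, but it would then be departing from the stated population.

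Third, section 19.1 also has the imaging committee review further images received during the study, and section 9.3 is not limited to the sub-study. Some main-study images may therefore be adjudicated, and the remit is ambiguous there. This reduces the inflation, as the runs with 10% and 25% detection show, but leaves ascertainment uneven. No such opening exists for the electrical committee.

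Fourth, inflation needs a case-mix difference, and the protocol does not show one. This stands: with equal prevalence there is none, at 35/30 it is slight, and the 44% figure needs a 20-point imbalance, 10% incidence and no outside detection together. A difference is nevertheless plausible. Section 4.5 expects about 55% to consent to a sub-study that fills by month 14, while main enrollment runs to month 24.

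Last, these are descriptive comparisons with few expected cases: 311 × 1% to 2% is about 3 to 6. That limits the consequence but does not repair the population.

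**Conclusion.** The concern holds. The stated population for 5.3.10 and 5.3.11 contradicts the sub-study scope and cannot be classified by the procedures the protocol provides. In 5.3.10, 76% of the named population have no scheduled imaging, and about 82% have no scheduled image once attrition before month 24 is counted (assuming constant-rate attrition). In 5.3.11 the affected patients are only the main-study leads taken out of service, about 76% of all such leads if rates are equal inside and outside the sub-study.

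The consequence is conditional. Under a moderate assumed imbalance (40% against 30%), the false-positive rate rises from a nominal 5% to about 7% to 16% in 5.3.10 and 7% to 11% in 5.3.11; without imbalance it does not rise. The primary endpoint, the complication-rate endpoint and both sample sizes are untouched. It should be corrected because p-values on lead and implant factors are promised and could be read as predictors of lead failure.

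**What to change.** Change the two population lines. In 5.3.10: sub-study patients with at least one adjudicated cinefluoroscopy. In 5.3.11: sub-study patients, which matches the electrical committee's remit in 19.2.

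Two refinements to 5.3.10 are worth considering. Requiring that the adjudicated image be a scheduled one would keep out patients whose only image was taken for cause. Reporting the number of images per patient in each group would show how far follow-up still differs, since one image and four images both qualify.

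No new data are needed. The cost is a smaller comparison group, about 311 patients in 5.3.10 and 417 in 5.3.11. Any case found for cause outside the sub-study would be described separately and not entered in the comparison.

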3.0 Description of Device

The Optisure HV lead is an 8 French, transvenous, steroid eluting, bipolar lead intended for the permanent sensing and pacing of the right ventricle, and the delivery of cardioversion/defibrillation therapy when used with a compatible SJM ICD or CRT-D device.

Optisure Model Number	Connector Type	Fixation	Single/Dual Coil
LDA220	DF-1/IS-1		
LDA220Q	DF4	Active	Dual
LDA230	DF-1/IS-1		
LDA230Q	DF4	Active	Dual
LDA210	DF-1/IS-1		
LDA210Q	DF4	Active	Single
LDP220	DF-1/IS-1		
LDP220Q	DF4	Passive	Dual
LDP230	DF-1/IS-1		
LDP230Q	DF4	Passive	Dual

As compared to the Durata leads, the Optisure HV dual coil leads have an increased Optim sheath thickness of $0.0070"$ (from $0.0035"$) between the connector boot and the SVC defibrillation coil. In order to accommodate the increase in the thickness of the Optim sheath, minor modifications have been made to increase the inner dimensions of the suture sleeve. The Optisure HV dual coil leads also have an Optim sheath underneath the SVC defibrillation coil. In order to accommodate the Optim sheath underneath the SVC defibrillation coil, the SVC defibrillation coil has an increased diameter of $0.100"$ (from $0.092"$).

As compared to the Durata leads, the Optim sheath thickness in the Optisure family of HV single coil leads has been increased by 0.0035" between the connector boot and the proximal portion of the lead body, which is 9.85" from the distal tip of the lead.

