Demographic and clinical parameters will be compared between patients who experience electrical dysfunction and those who do not experience electrical dysfunction. Specifically, the variables age, gender body mass index, lead size, lead model, and implant factors such as venous access site, number of other leads in the vasculature, fixation location in the right ventricle, level of activity (based on functional NYHA class scale I, II, III, IV), level of therapy that patient received (no ATP/shock, ATP or shock) and slack in the lead (grades 0, 1, 2, 3, 4 based on the scale described by Ha et al, 2010⁸) will be used for the comparison. Continuous variables such as age or body mass index will be compared using Student's T-tests while categorical variables such as gender or lead models will be compared using Pearson's Chi-square statistic. Point estimates and p-values will be provided from these analyses.

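### Sections 5.3.10 and 5.3.11 do not name coil number as a factor, although section 3.0 describes different construction for single-coil and dual-coil leads; *lead size* is undefined

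*Protocol*

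**What the plan says.** Section 5.3.10 compares patients who have lead compromise on imaging with those who do not. Section 5.3.11 does the same for electrical dysfunction. Each gives a specific list of variables: "the variables age, gender, body mass index, lead size, lead model, and implant factors" in 5.3.10, and "the variables age, gender body mass index, lead size, lead model, and implant factors" in 5.3.11. Both go on to venous access, other leads in the vasculature, fixation location, NYHA class, therapy received and slack. On the test they say that "categorical variables such as gender or lead models will be compared using Pearson's Chi-square statistic", and they promise point estimates and p-values. Fixation location is a position in the right ventricle, not the active or passive fixation method.

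Section 3.0 gives one diameter: "The Optisure HV lead is an 8 French, transvenous, steroid eluting, bipolar lead". Its table lists ten models by connector, fixation and a column headed "Single/Dual Coil". Two models are single-coil and eight are dual-coil. On construction it says that "The Optisure HV dual coil leads also have an Optim sheath underneath the SVC defibrillation coil", with a larger SVC coil to make room for it. For the other type it says that "the Optim sheath thickness in the Optisure family of HV single coil leads has been increased by" 0.0035 inch, between the connector boot and a point 9.85 inches from the distal tip.

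**The concern.** The protocol introduces the product by connector, fixation method and number of shocking coils, and tabulates the models on those three attributes. None of the three is a named factor in the comparisons meant to show which leads fare worse. Coil number matters most, because it is the attribute for which section 3.0 describes a difference in insulation and coil construction. The outcomes also follow coil anatomy. Section 2.0 lists internal abrasion under the SVC coil separately from abrasion under the RV coil, and Appendix A lists the SVC coil as an anomaly location. A single-coil lead has no SVC coil.

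As written, a single/dual difference can appear in a test only through *lead model*, where a two-level effect is spread over as many as nine degrees of freedom. A real difference by coil type could then yield an unremarkable p-value.

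**Working it through.** **Inputs from the protocol.** Ten models, two single-coil and eight dual-coil (3.0). Pearson's chi-square for categorical factors (5.3.10, 5.3.11). Sub-study enrollment of 417, to keep at least 200 patients with 60-month fluoroscopy after 52% attrition (4.3). The plan's own figure reproduces: 200 / (1 − 0.52) = 416.7, rounded up to 417. It states no power for the comparisons at issue. Both sections name all implanted patients as the population, but section 19 has both adjudications cover the sub-study, so 417 is the relevant size.

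**Assumptions not in the protocol.** Two-sided 5% level; all ten models in use, and equally used within coil type; single-coil share 20–50%; event rates as given below, with the higher rate in the single-coil group.

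**Step 1: structure of the model factor.** Ten models by two outcomes gives (10 − 1)(2 − 1) = 9 degrees of freedom, fewer if some models are not enrolled. The table has only six combinations of connector, fixation and coil number: active-dual, active-single and passive-dual, each with DF-1 or DF4. LDA220/LDA230, LDA220Q/LDA230Q, LDP220/LDP230 and LDP220Q/LDP230Q have identical entries. No single-coil passive model is listed.

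**Step 2: power at equal effect.** If the effect lies wholly in coil number, the noncentrality λ is the same for both tests. Power is P[χ²(df, λ) > c], with c = 3.84 on 1 df and 16.92 on 9 df.

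| λ | 1 df | 9 df |
|---|---|---|
| 3.84 | 50% | 22% |
| 6.00 | 69% | 34% |
| 7.85 | 80% | 45% |
| 10.51 | 90% | 59% |

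For 80% power on 9 df, λ must be 15.65. Since 15.65 / 7.85 = 1.99, the ten-level test needs about twice the patients.

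**Step 3: what this means at N = 417.** With single-coil share s, rates p₁ and p₀, and overall rate p̄, λ = N·s(1 − s)(p₁ − p₀)² / [p̄(1 − p̄)]. For s = 0.3 and rates of 10% and 5%: p̄ = 0.065, and λ = 417 × 0.21 × 0.0025 / (0.065 × 0.935) = 3.60. That gives 47% power on 1 df and 20% on 9 df. Over shares of 20–50%:

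| Rates | 1 df | 9 df |
|---|---|---|
| 1% vs 2% | 12–14% | 7% |
| 2% vs 4% | 19–23% | 9–10% |
| 5% vs 10% | 41–50% | 17–22% |
| 5% vs 15% | 89–94% | 58–67% |

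**Step 4: sparseness.** With ten equally used models, expected events per model are 417 × rate / 10: 0.4 at 1%, 0.8 at 2% and 2.1 at 5%. The 9-df approximation is unreliable at such counts. Simulation at N = 417 (20,000 runs; shares of 20% and 40%) gave 4–8% for 2% vs 4%, 13–17% for 5% vs 10% and 53–56% for 5% vs 15%. These are at or below the formula values.

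**The case against.** The strongest reply is that these are exploratory comparisons with no hypothesis, sample size or power claim. Event rates by model can be pooled by coil type afterwards, and the grouping of models may be left to an analysis plan that is not shown. The lack of a power claim stands and keeps the point minor. But the sections do fix the variable list, name lead models as an example for the chi-square test and promise p-values. A coil contrast pooled after the data are seen is not the same as one named beforehand.

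Three stronger readings are tempting, and the document does not support them:

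- **That the *lead size* comparison has no power at all.** This holds only if the term means diameter. It could mean length, which section 3.0 does not give. The 220/230 pairs with identical entries show that the table does not record everything that distinguishes the models. The supportable statement is that the term is undefined.
- **That the choice of factors is why power is low.** At N = 417 the 1-df coil contrast itself reaches at most about 50% for a doubled risk. Few events are the main limit, and the coding makes it worse.
- **That the model test should be replaced.** In a surveillance study it is the listed test that can pick up a defect confined to one model, and it keeps the 220/230 distinction.

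It is also fair to say that section 3.0 describes each type as a change from the Durata leads, and that the sheath increment is the same: 0.0070 − 0.0035 = 0.0035 inch for dual-coil, and 0.0035 inch for single-coil. The single/dual difference lies in the extent of the thicker sheath and in the SVC coil with the sheath beneath it.

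**Conclusion.** The point holds as a minor one. The only lead-design factors named are an undefined *lead size* and a ten-valued *lead model*. The attribute for which section 3.0 describes a construction difference is not named. For an effect that lies wholly in coil number, going from 1 to 9 degrees of freedom cuts power from 80% to about 45%, which is equivalent to needing about twice the patients.

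That ratio depends on the 5% level, on all ten models being enrolled, and on the effect being confined to coil number. The absolute figures at N = 417 depend further on assumed rates and model mix. A reader should not infer that adding the coil contrast would make the comparison well powered: for a doubled risk at base rates of 1–5% it would reach 12–50%, against 7–22% for the model test.

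**What to change.** In both 5.3.10 and 5.3.11:

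1. Add coil number (single or dual), derived from the recorded model number through the section 3.0 table, as a named 1-df factor.
2. Optionally add connector (DF-1 or DF4), and fixation method (active or passive). Restrict the fixation contrast to dual-coil leads, because no single-coil passive model is listed.
3. Keep the lead-model comparison.
4. State what *lead size* means, or drop it if it means diameter.

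This is a short edit in two sections and needs no new data. The downside is one or a few more exploratory p-values. If all three attributes were added and a Bonferroni level of 0.05 / 3 = 0.0167 were applied, the 80% at λ = 7.85 would fall to about 66%, still above the 45% of the ten-level test. Adding coil number alone would meet the concern.
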